| Statistical Considerations (sample size and analysis plan): | 
This is a cross-sectional pilot study. The mean shear wave velocity and elasticity and the mean values of serum biomarkers will be compared among the individual disorders (ASS1D, ARG1D, ASLD) and OTCD using a one-way ANOVA. Any correlation between the shear wave velocity and serum markers will be assessed by using appropriate correlation statistical methods. For the other disorders (CPS1D, NAGSD, citrin deficiency, and males with OTCD males,) we expect that sample size will be limited given that these disorders are ultra-rare or given that many patients receive early liver transplantation as part of routine management. Thus, data analysis for these other disorders will be descriptive only.
 
Published data demonstrate that the mean (SD) shear wave velocities in population without liver disease to be 1.56 (0.4) m/s. We would expect that individuals with OTCD would have values comparable to these values. In individuals with ASLD and ARG1D, we would expect higher shear wave velocities comparable to individuals with grade 2-3 liver fibrosis. The mean shear wave velocities (SD) grade 3 fibrosis is 2.57 m/s (0.3). We hypothesize that the mean shear wave velocity in ASS1D will be intermediate between ASLD/ARG1D and controls. Assuming a normal distribution for, with a sample size of 8 individuals per group, we will be able to detect a minimum difference in means of 0.79 m/s, when the standard deviation is 0.4 m/s, at an alpha error of 0.05 and a power of 0.8.
 |
| Sponsors (federal, state, foundation and industry support): | National Institutes of Health (NIH) |

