The purpose of this study is: 1) To determine whether liver stiffness is higher in individuals with ASS1D, ASLD, and ARG1D as compared to females with OTCD, and to assess liver stiffness in other UCDs (citrin deficiency, NAGSD, CPS1D, and males with OTCD), 2) To test whether markers of hepatocellular injury and function and novel serum biomarker panels for hepatic fibrosis provide evidence of chronic liver disease in individuals with ASS1D, ASLD, and ARG1D as compared to OTCD and to assess these sample markers of hepatocellular injury and function and novel serum biomarker panels for hepatic fibrosis in other UCDs (citrin deficiency, NAGSD, CPS1D, and males with OTCD).

2. Specific Aims (Hypothesis and Objectives)

Hypothesis:

We hypothesize that individuals with ASLD and ARG1D will have higher liver stiffness as assessed by non-invasive ultrasonographic techniques and greater serum biomarker evidence for fibrosis as compared to females with OTCD. We hypothesize that individuals with ASS1D will have liver stiffness and serum biomarkers that are intermediate between OTCD and the other two distal disorders (ASLD and ARG1D).

Study Objectives:

Specific Aim #1: To determine whether liver stiffness is higher in individuals with ASS1D, ASLD, and ARG1D as compared to females with OTCD, and to assess liver stiffness in other UCDs (citrin deficiency, NAGSD, CPS1D, and males with OTCD),

Specific Aim #2: To test whether markers of hepatocellular injury and function and novel serum biomarker panels for hepatic fibrosis provide evidence of chronic liver disease in individuals with ASS1D, ASLD, and ARG1D as compared to OTCD and to assess these sample markers of hepatocellular injury and function and novel serum biomarker panels for hepatic fibrosis in other UCDs (citrin deficiency, NAGSD, CPS1D, and males with OTCD).

We will conduct a pilot, cross-sectional study to assess liver stiffness and markers of hepatic injury, function, and fibrosis in patients with ASLD, ARG1D, ASS1D, and OTCD and in patients with other UCDs (citrin deficiency, NAGSD, CPS1D, and males with OTCD). This study will be conducted at 3 UCDC sites: Baylor College of Medicine in Houston, Texas, University of California San Francisco (UCSF), San Francisco, California and Seattle Children's Hospital, Seattle, Washington.

3. Background

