Recruitment will occur by physicians, study nurses, and research coordinators. Past and current patients of Drs. [name], [name], [name], [name], and [name] and subjects who have participated in previous studies may be contacted directly by study staff for possible recruitment. The study population may also include patients enrolled in the Urea Cycle Disorders Consortium Longitudinal Study or patients who have enrolled in other UCD studies. These patients may be recruited at routine study visits or through phone contact. The study will be posted on Clinicaltrials.gov. In addition, subjects may be recruited through advertisement by the National Urea Cycle Disorders Foundation. Details of the goals of the research and the risk and benefits of the protocol will be reviewed with each potential study participant. Strict patient confidentiality will be observed throughout all aspects of the study. Potential subjects may be requested to provide medical records prior to consenting to the study to establish eligibility. In this case, a medical records release form will be completed to request relevant medical records and laboratory data. While medical records will be reviewed by members of the research team, no individually identifiable patient data will be distributed to non-research or care-giving team members.

We plan to enroll n=8 subjects (male or female) with ASLD, n=8 subjects (male or female) with ARG1D, n=8 subjects (female) with OTCD, n=8 subjects (male or female) with ASS1D and a total of n=8 subjects with other UCDs (CPS1D, NAGSD,

citrin deficiency, and males with OTCD) across three study sites.

All study subjects must be 5 years of age or older. The projected enrollment at each site based on current patient population is provided in Table 1. These projected enrollment at each site is an estimate and may need to be adjusted based on actual enrollment.

Table 1. Projected study enrollment at each study site.

| Study Site | OTCD (Female) | ASLD | ARG1D | ASS1D | Other UCDs |
|-----------------------------------------------|------------------|----------|----------|----------|------------|
| Baylor College of Medicine | 3-5 | 5-6 | 4-6 | 6-7 | 6-7 |
| UCSF | 1-3 | 0-1 | 2-3 | 0-1 | 0-1 |
| Seattle Children's Hospital | 1-3 | 1-2 | 0-1 | 0-1 | 0-1 |
| Target Enrollment Across Sites | 8 | 8 | 8 | 8 | 8 |

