Chronic Liver Disease in Urea Cycle Disorders

ClinicalTrials.gov Identifier: NCT03721367

5-11-2022

Demographic characteristics, medical history, and liver biomarkers were summarized using means and standard deviations for continuous outcomes and counts and frequencies for categorical outcomes. For each outcome, we stratified subject characteristics summaries by normal or abnormal readings. For the strength of association between outcome measures and subject characteristics, univariate analyses were used (independent t-test for comparison of means and chi-square test for comparison of proportions). $P < 0.05$ (nominal) was considered as statistically significant. All statistical analyses were conducted using R or Graphpad Prism v.8.4.2 software (San Diego, CA).

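### The SAP's univariate tests of subject characteristics against normal/abnormal readings ignore disorder, so a pooled association may reflect disorder mix rather than the characteristic

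*SAP*

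**What the plan says.** The SAP is one paragraph. On grouping it says: "For each outcome, we stratified subject characteristics summaries by normal or abnormal readings". On testing it says that "univariate analyses were used (independent t-test for comparison of means and chi-square test for comparison of proportions". Results below a nominal P of 0.05 are called statistically significant. No stratification, regression or other adjustment for disorder is named.

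The protocol does not fill this gap. Its Synopsis (Statistical Considerations) says that mean velocity, elasticity and serum markers "will be compared among the individual disorders (ASS1D, ARG1D, ASLD) and OTCD using a one-way ANOVA". It also plans correlations between velocity and serum markers, and restricts the remaining disorders to description. None of these adjusts an association between a characteristic and a reading for disorder.

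Three statements in the protocol bear on the point:

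- Section 2 (Specific Aims): "We hypothesize that individuals with ASLD and ARG1D will have higher liver stiffness", with females with OTCD as the comparator.
- Synopsis, on OTCD and the reference velocities: "We would expect that individuals with OTCD would have values comparable to these values". On the distal disorders: "In individuals with ASLD and ARG1D, we would expect higher shear wave velocities comparable to individuals with grade 2-3 liver fibrosis".
- Section 4.3 (Recruitment): "n=8 subjects (female) with OTCD, n=8 subjects (male or female) with ASS1D". ASLD and ARG1D also take either sex, and a fifth group of 8 covers the other UCDs, including males with OTCD.

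**The concern.** The plan expects disorder to determine the reading. If a characteristic also differs by disorder, pooling all disorders links that characteristic to the reading even when it has no effect inside any of them. The chi-square and t-test results in the SAP cannot separate the two explanations.

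Sex is the clearest case because the protocol itself fixes part of the imbalance: the group expected to have near-normal stiffness contains no males. The SAP does not name sex, but it summarises demographic characteristics, so a test of sex is a reasonable reading. The same mechanism applies to any other characteristic whose distribution differs by disorder.

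What is at stake is interpretation. A result called significant could be reported as a risk factor for liver involvement when it only restates which disorders were enrolled.

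**Working it through.** The documents give no figure for this analysis. The protocol's detectable difference of 0.79 m/s belongs to the comparison between disorders and is not used here. (It is close to a two-sided t-test with Bonferroni correction for six pairs: 0.797 m/s at 80% power.)

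**Inputs from the protocol.** Reference and expected OTCD velocity: mean 1.56, SD 0.4 m/s. Grade 3 fibrosis: mean 2.57, SD 0.3. ASS1D intermediate. Eight subjects per group, with OTCD all female.

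**Assumptions.**
- There is no sex effect inside any disorder.
- ASLD, ARG1D and ASS1D each have 4 males of 8.
- The ASLD/ARG1D mean is 2.20-2.57, since the protocol expects grade 2-3 but gives only grade 3. Their SD is 0.3 or 0.4.
- ASS1D lies at the midpoint between 1.56 and the ASLD/ARG1D mean, SD 0.4.
- Abnormal means above 2.34 m/s, the 97.5th percentile of the reference (1.56 + 1.96 × 0.4 = 2.34). The SAP gives no cut-off.

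**Step 1: abnormal rate per disorder**, p = 1 − Φ((2.34 − mean)/SD).

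| | Mean 2.57, SD 0.3 | Mean 2.20, SD 0.3 |
|---|---|---|
| OTCD: z = (2.34 − 1.56)/0.4 = 1.95 | 2.6% | 2.6% |
| ASS1D (mean 2.065; 1.88) | z = 0.69, 24.6% | z = 1.15, 12.5% |
| ASLD, ARG1D | z = −0.77, 77.8% | z = 0.47, 32.0% |

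**Step 2: pooled rates by sex, four groups** (20 females, 12 males).
- Mean 2.57: females (8 × 0.0256 + 4 × 0.2459 + 8 × 0.7784)/20 = 7.416/20 = 37.1%; males (4 × 0.2459 + 8 × 0.7784)/12 = 7.211/12 = 60.1%. The gap is 23 points.
- Mean 2.20: females (0.205 + 0.500 + 2.563)/20 = 16.3%; males (0.500 + 2.563)/12 = 25.5%. The gap is 9 points.

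The odds ratio inside every disorder is 1 in both cases.

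**Step 3: rejection by the pooled chi-square.** Sum P(F = i) × P(M = j) over all 2×2 tables with P < 0.05, where F and M are the abnormal counts in each sex, each a sum of independent binomials. Over the stated means and SDs this gives 10.3-19.0% (4.0-8.4% with Yates). With equal abnormal rates of 10-75% in all disorders, the same test rejects in 2.5-4.9% (0.5-2.0%).

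**Step 4: all 40 subjects.** Add the other UCDs with 4-6 males of 8 and an assumed abnormal rate anywhere from the OTCD rate to 50%. Rejection is about 2-18% (0.4-9% with Yates). The two ends, both at mean 2.57 and SD 0.3:
- Low end, 6 males with OTCD-like rates: females (7.416 + 2 × 0.0256)/22 = 33.9%, males (7.211 + 6 × 0.0256)/18 = 40.9%.
- High end, 5 males with a 50% rate: females (7.416 + 1.5)/23 = 38.8%, males (7.211 + 2.5)/17 = 57.1%.

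If all 8 were males with OTCD-like readings, the male rate would be (7.211 + 8 × 0.0256)/20 = 37.1%, equal to the female rate, and the distortion would cancel.

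**Step 5: sensitivity, four groups, cut-offs 1.76-2.34.** With 4 males per mixed group: 10-30% (4-17% with Yates). With 3: 7-19% (2-7%). With 5: 12-52% (3-34%).

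**Step 6: stratified by disorder.** The Cochran-Mantel-Haenszel variance of a stratum is n₁n₂m(T − m)/(T²(T − 1)), where n₁ and n₂ are the numbers of each sex, m the abnormal count and T the total. It is zero for OTCD females because there are no males, which leaves 12 v 12. Over the same cut-offs the test rejects in 2.6-5.7% with no sex effect. Its power is about 3-46% for a within-disorder odds ratio of 5 and 3-74% for 10.

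**The case against.** The strongest reply is that the SAP does not confine this analysis to four groups. All 40 subjects may be in it, and the fifth group names males with OTCD, who can offset the all-female comparator. With Yates the 40-subject range is 0.4-9%, which spans the nominal 5%, and the SAP does not say which form of the chi-square was used. This stands: the size and even the presence of a sex distortion depend on who enrols.

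A second reply is that the tests address association in the pooled sample. If disorder mix makes the pooled rates differ by sex, that association is real and rejecting is correct. This also stands. The percentages above show how often a reader would meet such a result; they are not false-positive rates for the pooled hypothesis.

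Third, the P values are called nominal, the study is a pilot, sex is not named, and the undefined set of subject characteristics might include disorder itself. These points lower the weight. They do not remove the confounding, because the SAP still declares significance, and testing disorder as one more univariate factor adjusts nothing.

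A reader might infer that the design builds in a sex bias that produces spurious findings in about 30% of studies. The documents do not support that. The figure needs only the four groups and a cut-off near 1.82 m/s, which would call about 26% of the reference population abnormal (z = (1.82 − 1.56)/0.4 = 0.65). The primary outcome is a Z-score, so a reference limit near 2.34 is the more natural choice. Nor does the point undermine the primary comparison: the ANOVA compares disorders directly and does not use these tests.

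**Conclusion.** The omission is real. Neither document adjusts the association between a characteristic and a reading for disorder, although the protocol expects disorder to drive stiffness. A pooled result is sound as description but cannot show that a characteristic matters apart from disorder.

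For sex, the effect ranges from none to moderate once all 40 subjects are included, and is clearer in the four groups the protocol tests. Both ranges rest on the assumed cut-off, sex split and group means, and cover shear wave velocity only. No figure was derived for other characteristics or for the serum markers; for those the argument is qualitative.

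Severity is minor to moderate: this is a nominal, secondary analysis in a pilot, and the risk is misinterpretation rather than a wrong primary result.

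**What to change.** 1. Tabulate subject characteristics and normal/abnormal readings by disorder.
2. In the four groups the protocol tests (ASS1D, ARG1D, ASLD, OTCD females), add a disorder-stratified or disorder-adjusted analysis: Cochran-Mantel-Haenszel or an exact stratified test for categorical characteristics, and a model with disorder as a factor for continuous ones.
3. Label the pooled univariate P values descriptive. Do not claim, on a pooled P value alone, that a characteristic is associated with abnormal readings independently of disorder.
4. The SAP is dated 5-11-2022 and written in the past tense. If the analyses are complete, label the addition post hoc.

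The cost is a little analysis time in R, which the SAP already names, and no new data. The drawback is low power: OTCD females carry no information on sex, so a non-significant stratified result is inconclusive and should be reported as such. The table by disorder and the descriptive label are worth having even if the stratified test adds little.

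### The SAP does not say whether its t-test pools the variances; if it does, unequal normal and abnormal groups can move the error rate well away from 5% in either direction

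*SAP*

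**What the plan says.** The SAP is a single section. For each outcome, "we stratified subject characteristics summaries by normal or abnormal readings", and for association it states that "univariate analyses were used (independent t-test for comparison of means and chi-square test for comparison of proportions", at a nominal 0.05 level. On software it says only that "All statistical analyses were conducted using R or Graphpad Prism v.8.4.2 software". It does not state the pooled or unequal-variance form, which package ran which test, the cut-off for an abnormal reading, or the number of subjects on each side.

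The protocol gives the planned numbers in section 4.3: "We plan to enroll n=8 subjects (male or female) with ASLD, n=8 subjects (male or female) with ARG1D", 8 females with OTCD, 8 with ASS1D, and "a total of n=8 subjects with other UCDs". That makes 5 x 8 = 40. The Statistical Considerations in the synopsis (section 1) give the only two SDs in the documents, both for shear wave velocity. One is 0.4 m/s without liver disease; the other comes from the statement "The mean shear wave velocities (SD) grade 3 fibrosis is 2.57 m/s (0.3".

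**The concern.** The pooled t-test estimates one common variance, and the larger group dominates that estimate. If the smaller group is the more variable, the standard error comes out too small and the test rejects too often. If the smaller group is the less variable, the standard error is too large and the test rejects too rarely. Normal data do not protect against this, and it matters most when the groups are unequal in size.

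A split by reading is not balanced by design, and it is redone for each outcome. The protocol describes hepatic complications in a subset of patients (sections 1.1 and 3) and calls routine liver tests possibly insensitive (section 3). Small abnormal groups are therefore plausible for some markers. What is at stake is whether the 0.05 threshold means what it says for these comparisons, and whether a reader can tell which p-value was computed.

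**Working it through.** **Inputs.** From the documents: N = 40, nominal level 0.05, and an SD ratio (abnormal/normal) of 0.3/0.4 = 0.75 for shear wave velocity. Assumed, because the documents are silent: a two-sided test, normal data, equal true means, 4 to 24 abnormal subjects, and other SD ratios from 1 to 3.

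**The plan's own figure.** The only error rate stated is the nominal 5%. The pooled test reproduces it at every split when the SDs are equal (ratio 1 in the table). The detectable difference of 0.79 m/s in the synopsis belongs to the ANOVA across disorders and does not bear on this point.

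**Mechanism.** Let n1 be the abnormal group, n2 the normal group and r the SD ratio, with the normal SD set to 1.

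- True variance of the difference in means: r²/n1 + 1/n2
- Variance the pooled test uses, on average: [(n1 − 1)r² + (n2 − 1)]/(n1 + n2 − 2) × (1/n1 + 1/n2)

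*4 vs 36, r = 2.* True: 4/4 + 1/36 = 1.0278. Pooled: (3 × 4 + 35)/38 × (1/4 + 1/36) = 1.2368 × 0.2778 = 0.3436. The standard error is √(0.3436/1.0278) = 0.578 of what it should be. The critical value 2.024 (38 degrees of freedom) then acts like 2.024 × 0.578 = 1.17, a two-sided normal tail of about 24%.

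*4 vs 36, r = 0.75.* True: 0.5625/4 + 1/36 = 0.1684. Pooled: (3 × 0.5625 + 35)/38 × 0.2778 = 0.2682. The standard error is √(0.2682/0.1684) = 1.26 times too large, the critical value acts like 2.55, and the tail is about 1%.

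**Simulation.** These approximations ignore the sampling error of the variance, so the rates were simulated (400,000 null data sets per cell). False-positive rate of the pooled test, in %, with the range for Welch's test over the same ratios:

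| Abnormal vs normal | r = 0.75 | r = 1 | r = 1.5 | r = 2 | r = 3 | Welch, all r shown |
|---|---|---|---|---|---|---|
| 4 vs 36 | 1.5 | 5.0 | 15.4 | 25.0 | 38.1 | 5.4-6.3 |
| 10 vs 30 | 2.5 | 5.0 | 10.8 | 15.5 | 21.1 | 5.1-5.2 |
| 16 vs 24 | 3.9 | 4.9 | 7.0 | 8.6 | 10.2 | 4.9-5.1 |
| 20 vs 20 | 5.0 | 5.0 | 5.1 | 5.2 | 5.4 | 4.9-5.0 |
| 24 vs 16 | 6.4 | 5.0 | 3.5 | 3.0 | 2.4 | 4.9-5.0 |

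Welch's test is not exact in very small groups: at 3 vs 37 it runs at about 6-8%.

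**Cost in power.** With equal SDs and a true difference of 1 SD, power falls from about 53% (pooled) to 41-42% (Welch) at 5 vs 35, and from 76% to about 72.5% at 10 vs 30.

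**The case against.** A reader might infer that the SAP runs a pooled test on a small abnormal group, so that its false-positive rate is 11-38%. The documents do not support that. The word independent only separates the test from a paired one; Welch's test is also an independent-samples test and may be what was run. No group sizes are given. For stiffness, the protocol expects higher values in ASLD and ARG1D (16 of 40) and intermediate ones in ASS1D (8 more), which suggests 16 to 24 abnormal, a range where distortion is modest. An abnormal SD 1.5 to 3 times larger appears nowhere. The protocol's one pair of SDs points the other way, to a conservative test whenever the abnormal group is the smaller one. Those SDs also describe shear wave velocity, an outcome that may itself define the groups, and not the characteristics being compared.

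All of this stands, and it makes the size of the problem conditional. It does not remove the gap. The SAP's wording fits two tests that behave very differently at this sample size, and the documents exclude neither direction of error for the variables compared. That the trial is a pilot with nominal p-values lowers the stakes, but a nominal 5% should still be close to 5%.

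Extending the change to the ANOVA across disorders would also go too far. Those groups are planned at 8 each, so the imbalance that drives the problem is absent by design.

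**Conclusion.** The point holds as an unspecified choice with conditional consequences. If the variances were pooled among 40 subjects with 4 to 10 abnormal, the error rate is about 11-38% at an abnormal SD 1.5 to 3 times larger, and about 1.5-2.5% at the ratio of 0.75. At 16 vs 24 the figures are 7-10% and about 4%. With equal group sizes or equal SDs it is about 5%. The pooling, the group sizes and every SD ratio other than 0.75 are assumptions, and applying 0.75 to variables other than shear wave velocity is also one.

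It would be wrong to conclude that every mean comparison in the SAP is invalid, or that reported findings are false positives. Confidence is high in the ambiguity and the mechanism, and limited in the size that applies to this trial. This is an inexpensive improvement, not a fundamental flaw.

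**What to change.** In the SAP, replace the reference to an independent t-test with Welch's unequal-variance t-test for every two-group comparison of means, whether run in R or in Prism. Rerun any comparison that used the pooled form and note any result that crosses 0.05 as a consequence. Leave the ANOVA across disorders as it is.

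The text change is minimal and no new data are needed. If Welch's test was already used, nothing has to be rerun. The statistical cost is the power loss shown above, appreciable with about 5 abnormal subjects and small with 10, and an error rate of about 6% when a group has 4 or 5 subjects.

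### The SAP's chi-square test has no rule for sparse tables: with about 40 subjects, one subject can give uncorrected P<0.05 where the exact P is 0.125 to 0.20

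*SAP*

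**What the plan says.** The SAP is one paragraph in the past tense. For each outcome, "we stratified subject characteristics summaries by normal or abnormal readings". Characteristics are then related to outcomes one at a time, by a t-test for means and a "chi-square test for comparison of proportions", at a nominal threshold of P<0.05. On computing it says: "All statistical analyses were conducted using R or Graphpad Prism v.8.4.2 software". Nothing says which form of the chi-square test was run or what was done when expected counts were small.

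Protocol section 4.3 sets the numbers: "We plan to enroll n=8 subjects (male or female) with ASLD, n=8 subjects (male or female) with ARG1D, n=8 subjects (female) with OTCD", and "n=8 subjects (male or female) with ASS1D and a total of n=8 subjects with other UCDs". That makes 5 × 8 = 40 planned subjects. CPS1D, NAGSD, citrin deficiency and males with OTCD share the last eight places. Neither document gives the number of abnormal readings for any outcome, and the SAP does not give the number analysed.

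**The concern.** The chi-square P value is a large-sample approximation. With 40 subjects, a small abnormal stratum and an uncommon characteristic, such as a rare item of medical history, expected counts can fall well below 1. The uncorrected P value can then be several times too small.

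One subject could be enough for a characteristic to be reported as significantly associated with abnormal liver stiffness or an abnormal biomarker. In a pilot study of very rare disorders, such a finding could be carried into later work. Because the form of the test is not stated, the same table could also be reported as significant or as clearly non-significant under the same plan.

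**Working it through.** **The plan's own figure.** The only computed design figure concerns means: "with a sample size of 8 individuals per group, we will be able to detect a minimum difference in means of 0.79 m/s". Two-sided t-tests with Bonferroni adjustment for six pairwise comparisons give 0.797 m/s, and power 0.792 at 0.79 m/s, so it reproduces closely under an adjustment the protocol does not mention. It does not bear on the chi-square test, for which no figure is given.

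**Inputs.** N = 40 (protocol 4.3) and threshold 0.05 (SAP). The number abnormal, *m*, is an assumption: 5 to 8 is the main case, and 1 to 16 is covered below.

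**One subject with the characteristic, who is abnormal.** The table is 1 of *m* against 0 of 40 − *m*. With cells a = 1, b = *m* − 1, c = 0 and d = 40 − *m*, ad − bc = 40 − *m*.

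- Uncorrected: X² = 40(40 − m)² / [m(40 − m)·1·39] = 40(40 − m)/(39m). This exceeds 3.841 when 1600 − 40m > 149.8m, so m < 8.43, that is, 8 or fewer abnormal.
- Yates: X² = 40(|40 − m| − 20)² / [m(40 − m)·39].
- Fisher, two-sided: P = m/40.
- Smallest expected count: m/40.

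For m = 8, uncorrected X² = 40·32²/9984 = 4.10 (P = 0.043), Yates X² = 40·12²/9984 = 0.58 (P = 0.45), and Fisher P = 8/40 = 0.20.

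| Abnormal of 40 | Uncorrected P | Yates P | Fisher P |
|---|---|---|---|
| 4 | 0.0024 | 0.18 | 0.100 |
| 5 | 0.0074 | 0.25 | 0.125 |
| 6 | 0.016 | 0.32 | 0.150 |
| 7 | 0.028 | 0.39 | 0.175 |
| 8 | 0.043 | 0.45 | 0.200 |
| 9 | 0.060 | 0.50 | 0.225 |
| 10 | 0.079 | 0.56 | 0.250 |

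For 1 to 4 abnormal the Fisher P is 0.025 to 0.10, so the disagreement narrows and at m = 1 both tests are below 0.05. Other totals behave alike: with N = 36 and 5 to 7 abnormal the exact P is 0.139 to 0.194, and with N = 42 and 5 to 8 abnormal it is 0.119 to 0.190.

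**Overall type I error.** With the same prevalence π in both strata, sum Bin(a; m, π)·Bin(c; N − m, π) over every table with P<0.05. For the uncorrected test at N = 40 and π = 5%:

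| Abnormal | 4 | 5 | 6 | 8 | 9 | 10 | 12 | 16 |
|---|---|---|---|---|---|---|---|---|
| Error, % | 4.1 | 5.4 | 6.6 | 8.6 | 2.0 | 2.3 | 3.6 | 1.3 |

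At 3% prevalence, 8 v 32 gives 9.0%. At N = 32 and 5% prevalence, 6 v 26 gives 8.2% but 8 v 24 gives 2.0%. For prevalences of 15% to 50% the rate is about 3% to 6%. At 5% prevalence Fisher's test gives 1.5% (8 v 32), 0.7% (6 v 34) and 1.0% (6 v 26).

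**Larger tables.** If diagnosis (five groups of 8) is cross-tabulated with reading, the smaller expected count in any group is at most 8 × 20/40 = 4, so every such table has expected counts below 5. That alone does not create false significance. With all abnormal readings in one group, one abnormal gives chi-square P = 0.39. Two give 0.077 (exact 0.18), and three give 0.011 (exact 0.028).

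**The case against.** **The abnormal count is assumed.** The Protocol Synopsis expects ASLD and ARG1D to show stiffness like that of grade 2-3 fibrosis, and 16 such subjects are planned. If about 16 of 40 were abnormal on stiffness, one abnormal subject with the characteristic would give uncorrected P = 0.215, and the error at 5% prevalence would be 1.3%. This stands for the primary outcome. It does not settle the serum markers, each of which has its own split.

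**The test may have been corrected.** R's default for a 2×2 table applies Yates correction and warns when the approximation is doubtful, which would remove the effect for 5 to 8 abnormal. This stands too, but the SAP allows two programs and states no option. With 8 abnormal, the same table is P = 0.043 or P = 0.45 depending on a choice that is not recorded.

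**The step is a nominal univariate screen in a pilot.** The protocol's stated group comparison is of means. That limits the weight of the point but does not justify a P value several times too small.

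**Stronger readings to avoid.** A reader might infer a false-positive rate of 12.5% to 20%. Those figures apply only when exactly one of the 40 subjects has the characteristic; averaged over all tables at 5% prevalence, the highest rate is 8.6%. A reader might also infer that chi-square is wrong throughout the SAP, or that a reported result is false. The test is near nominal for commoner characteristics, and the documents contain no results from which to tell.

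**Conclusion.** The concern holds in a limited form. The SAP's method, as written, permits a falsely significant result from one subject and leaves open a software option that can reverse the conclusion. The size depends on three assumptions: the uncorrected test was used, 5 to 8 of 40 readings were abnormal for the outcome, and about 40 subjects (the planned number) were analysed. Under these, uncorrected P = 0.007 to 0.043 stands against exact P = 0.125 to 0.20. With 9 or more abnormal, or with Yates correction, that false significance does not occur. Across 3 to 16 abnormal at 5% prevalence, the overall error is about 1.3% to 8.6%, so in some configurations it is below nominal. The point matters for sparse tables only, and it should be corrected because the remedy is cheap.

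**What to change.** Add to the SAP that tables with small expected counts are tested by Fisher's exact test or its mid-P version, and by the Fisher-Freeman-Halton test when larger than 2×2. State the trigger: at the least any expected count below 1; conventionally, any below 5. The below-5 rule is simple but broad. With fewer than 10 abnormal of 40, no 2×2 table has all expected counts at 5 or more, so Fisher's test would also replace chi-square where the latter is near nominal. State whether a continuity correction was used.

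The SAP describes analyses already done, so an edit alone is not enough: re-run the affected tables and disclose every P value that crosses 0.05 in either direction, labelled as a retrospective check.

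The cost is a sentence or two and a re-run on existing data. Fisher's test is conservative: its actual error is about 0.3% to 4.2% for 3 to 12 abnormal at 5% to 50% prevalence (N = 40 or 32), so some power is lost. Mid-P recovers most of that but gives up the guarantee on the error rate. For the single-subject table it is half the Fisher P, m/80: 0.0625 to 0.10 for 5 to 8 abnormal, but 0.0375 for 3. The choice between the two should be stated before the re-run.
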